- **Inclusion Criteria:** Women in any stage of labor in participating facility who consent to observation of their delivery and care of their newborn (or consent from the next of kin if the woman is incapacitated and not able to provide consent)
- **Exclusion Criteria:** none

Facility In-charges and Stakeholders

- **Inclusion Criteria:** Facility in-charges at sampled health facilities; stakeholders identified by Jhpiego senior managers as being influential in maternal and newborn health policy decisions in Uganda.
- **Exclusion Criteria:** none

c. Provide **sample size** and a **justification** as to how you arrived at your projected sample size.

The total sample size for this study is 4683 - 2604 health care providers plus 2079 laboring women.

Knowledge and Competency Assessments

For the knowledge and clinical practice assessment, we propose conducting a census of birth attendants working at each facility on the days of training and midline and endline facility data collection. In training interventions, it is routine to test participants before and after the intervention in order to give them feedback to clarify any misunderstandings and improve their performance. We will also do these assessments at baseline and midline facility data collection because we are also interested in collecting data from all providers so that we can do a secondary analysis that will test for a correlation between providers' performance on knowledge assessments and simulator-based performance tests, participation in practice sessions, and directly observed clinical performance. Table 3 presents the maximum number of providers in

the sample facilities, based on data provided by the Ministry of Health; actual enrolled numbers will be lower because not all health care providers on staff will present on the day of data collection. **In addition, we recognize there will be overlap between providers at each time point.** The outcome measure will be a continuous variable measuring ‘correct’ knowledge and competencies across three OSCE exams of BAB or HBB.

Table 3. Number of Providers to be Assessed (c)

Region	Pre and post BAB training (a)	Pre and post HBB Training (a)	Midline Assessment (b) (d)	Endline Assessment (b) (d)	Total Providers in each study group (e)
Districts in Eastern	253	253	253	253	1012
Districts in Western	398	398	398	398	1592
Grand Total	651	651	651	651	2604

Notes

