- (a) Pre- and post-training, providers will be assessed on knowledge and OSCE competency tests. There will be separate one-day trainings for BAB & HBB spaced 2 months apart.
- (b) At midline and endline providers will be given BAB and HBB knowledge tests and OSCE skills tests. Facility readiness assessments will also occur at these time points.
- (c) The number of providers in this table is taken from the ACTUAL number of providers that we are aware exist in the Eastern and Western region that attend births. All providers are invited to participate in the intervention and may be assessed.

Direct Clinical Observation: Number of births (women and newborns) to be observed

We specify the sample size of number of births to observe below. The outcome variable is: the percentage of women who **received oxytocin** in correct dose immediately after vaginal birth in three study arms. The hypothesized levels of this variable at each time point are presented below:

Table 4. Hypothesized levels of “percent of women who **received oxytocin** in correct dose “within 1 minute of vaginal birth” in three study arms

Study Arm	Baseline	Midline	Endline
Full	50% (a)	75%	70%
Partial	50%	65%	60%
Training-only	50%	55%	50%

Note:

- (a) A study carried out in 2007 (POPPHI, 2007) found that **20%** of women delivering at health facilities in Uganda received an oxytocin injection between birth and the delivery of the placenta. However, given the small sample size (n=259 births observed) and the fact that the situation may have improved (as it has in many countries), we have conservatively estimated baseline coverage of oxytocin use to be **50%**.

Table 5. Number of **births** to observe (women in labor and delivery)

Study Arm	Baseline	Midline	Endline	Total births
Full Intervention Group (expected: 50% at baseline to 75% at midline to 70% at endline)	189 67 to compare baseline-midline	378 (a) for midline-endline comparison 99, midline-only comparison 67 to compare baseline-midline	378 (a) for midline-endline comparison 189 endline-only (b)	1134
Partial Intervention Group (expected: 50% at baseline to 65% at midline to 60% at endline)	189 to compare baseline-midline	189 , to compare baseline-midline 99, midline-only comparison	189 , endline-only comparison (b)	567
Training-only Group (expected: 50% baseline to 55% at midline to 50% at endline)	189	189 , midline-only comparison	189 , endline-only comparison (b)	567
Grand Total	567	756	756	2079

Notes

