- (a) The number of **378 births** is recommended for each time point in the full package group only. N=378 is based on calculations for midline and at endline is based on a (within-group) non-inferiority calculation in the intervention group. We set the number of health facilities at 54 (9 facilities on average per district * 3 districts * each of 2 regions). This sample size will achieve 80% power to detect a non-inferiority margin difference between the group proportions of providing oxytocin of -0.1000. As shown in the previous table, the percent of deliveries with oxytocin provision at midline (post-intervention) is hypothesized to be 70% in Full group. We assume intra-class correlation (ICC) of 0.005 and significance level of the test is 0.0250.
- (b) The number of **189 births** in each group at endline (only) is based on the following assumptions: This is a two-sample comparison of proportions. We aim to detect a 15% point difference at endline between an intervention group and the training-only group. Training-only group value set at 50%, as this is most conservative. Intervention group value set at 65%. Power is set at 80%. ICC is set at 0.01.
- (c) To avoid oversampling, and to compensate for different caseloads at different facilities, the study team will be given a target number of births to observe and they will stop when they reach this target. There will be no overlap in the number of women observed, because different women will be observed at different time points.

Service Statistic Data Abstraction

There is no sample size calculation for analysis of service delivery statistics because baseline data from the study health facilities are not available.

Qualitative Data: Focus Group Discussions and In-depth Interviews

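### Table 5: the full-arm row total of 1134 births does not match its cells (945), so the row totals give 2268 women against the 2079 stated; the full-arm baseline target needs confirming

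*Combined protocol and SAP*

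**What the plan says.** Section 3c gives the overall sample size as 4683, made up of "2604 health care providers plus 2079 laboring women". Table 5 divides the 2079 births by arm and time point. In the full-arm row, labelled "Full Intervention Group (expected: 50% at baseline to 75% at midline to 70% at endline":

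- the baseline cell reads "189 67 to compare baseline-midline";
- the midline cell reads "378 (a) for midline-endline comparison 99, midline-only comparison 67 to compare baseline-midline";
- the endline cell and the row total read, in part, "189 endline-only (b) 1134", after a leading figure of 378.

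The partial and training-only rows have 189 births at each time point and a row total of 567 each. The grand-total row is 567, 756, 756 and 2079.

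Note (a) to Table 5 first recommends 378 births for every time point in the full arm. Its next sentence ties that number to the non-inferiority calculation between midline and endline. Note (c) says of the field work that "the study team will be given a target number of births to observe and they will stop when they reach this target", and that different women are observed at each time point.

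**The concern.** A two-way table must reach the same grand total by rows and by columns, and this one does not. The figure affected is the number of women to be observed, which is also the number declared in the ethics submission. The mismatch also exposes a real ambiguity: the baseline cell and the opening of note (a) give different baseline numbers for the full arm, 189 and 378. Because observation stops when a target is reached, the baseline target should be beyond doubt before that round is carried out.

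**Working it through.** **Inputs.** All come from Table 5 and the sample-size statement in Section 3c. The leading number in each cell is the target. The smaller numbers beside it (67, 99, and 189 at endline in the full arm) are the needs of other comparisons, which the leading number already covers. Cells within a row can be added, because note (c) says that no woman is observed at more than one time point.

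**Step 1: the column totals, which reproduce.**
- Baseline: 189 + 189 + 189 = 567, as printed.
- Midline: 378 + 189 + 189 = 756, as printed.
- Endline: 378 + 189 + 189 = 756, as printed.
- Grand total: 567 + 756 + 756 = 2079, as printed.
- Section 3c: 2604 + 2079 = 4683, as printed.

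These sums work only with the leading numbers, which confirms how the cells are to be read.

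**Step 2: the row totals.**
- Partial and training-only: 3 × 189 = 567 each, as printed.
- Full: 189 + 378 + 378 = 945, against 1134 printed. Difference: 1134 − 945 = 189.
- Printed row totals: 1134 + 567 + 567 = 2268, against 2079. Difference: 189.
- With 945: 945 + 567 + 567 = 2079, which agrees.

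**Step 3: where 1134 could come from.**
- 3 × 378 = 1134. This needs 378 at baseline, where the cell says 189.
- 189 + 378 + 378 + 189 = 1134. This counts the endline-only 189 on top of the 378 that contains it, and breaks the endline column total of 756.
- Adding every number listed in the row gives 189 + 67 + 378 + 99 + 67 + 378 + 189 = 1367, which is not 1134.

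The first source is the more plausible, because it follows the opening wording of note (a).

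**Step 4: does anything in the plan need 378 at baseline?** The only baseline comparison listed for the full arm needs 67 births, and 189 covers that. The 378 is derived for midline against endline. In Section 4b5, hypotheses 1 and 2 compare midline with endline, and hypotheses 3 and 4 use endline data only. None of the four uses baseline births.

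**Step 5: size.** 189 / 945 = 20% of the full-arm total on the printed cells, and 189 / 2079 = 9% of all births.

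**Step 6: the alternative.** If 378 was meant at baseline, the baseline column becomes 378 + 189 + 189 = 756, the grand total 756 + 756 + 756 = 2268, and the overall sample size 2604 + 2268 = 4872. The row total of 1134 would then stand.

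**The case against.** The best defence of 1134 is that it has a source in the plan. Taken alone, the first sentence of note (a) asks for 378 births at all three time points in the full arm, and that makes 1134. Nor is the agreement of the other totals with 945 fully independent evidence: the baseline column total and the grand total follow from the same baseline cell, and Section 3c repeats the grand total. This part of the objection stands. It means that the contradiction is certain, while the direction of the correction is only likely. It does not rescue the table, which is inconsistent under either reading.

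A reader might also infer that field teams have two competing targets, 945 and 1134, and could observe 189 surplus women. The documents do not support that. Births are observed in separate rounds, so a workable target belongs to a round and not to the sum of three. Note (c) does not say that the row total is the target. The midline and endline cells are unambiguous and match their column totals. The only operational doubt is the full-arm baseline round: 189 or 378.

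Finally, a reader might infer that the trial's power is in question. It is not affected by this error: notes (a) and (b) justify 378 and 189 for the midline and endline comparisons, and neither calculation uses the row total.

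Damage in reading the PDF is an unlikely explanation. Every other total reconciles with the cells as read, and 1134 is an exact multiple of 378.

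**Conclusion.** The table is wrong as written. The full-arm row total exceeds the sum of its cells by 189 births, and the row totals give 2268 women where the plan states 2079.

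The better-supported correction is 945. It fits the baseline cell, all three column totals, the grand total, the Section 3c text, and the link that note (a) itself makes between 378 and midline and endline. This rests on the baseline cell of 189 being the intended number, which only the sponsor can confirm. The 20% figure likewise takes 945 as the correct total.

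The point is minor. It concerns a stated sample size and one baseline target, and leaves the margin, the power and the planned analyses untouched.

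**What to change.** The sponsor should confirm the full-arm baseline target, then make one of two sets of changes.

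- **If it is 189 (likely):** change the full-arm row total in Table 5 from 1134 to 945, and reword note (a) so that 378 applies to midline and endline only. The cost is one cell and one phrase. No other number changes.
- **If it is 378:** change the full-arm baseline cell to 378, the baseline column total to 756, the grand total to 2268, the number of women in Section 3c to 2268 and the overall sample size to 4872. The cost is these edits plus 189 more observed births at baseline, and the number of women declared to the ethics boards rises accordingly.

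Neither option changes the midline or endline targets or the analysis.

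### Table 5 sizes the partial arm for larger effects than Table 4 expects: the 99 at midline fits the full arm's contrast, and 189 births per arm give about 50% power for Hypothesis 3

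*Combined protocol and SAP*

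**What the plan says.** Section 3c sets expected rates for the oxytocin outcome in Table 4 and observed-birth targets in Table 5.

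- **Partial row of Table 5.** The label repeats the Table 4 rates: "Partial Intervention Group (expected: 50% at baseline to 65% at midline to 60% at endline". The baseline cell reads "189 to compare baseline-midline". The midline cell lists 189 births and also "99, midline-only comparison". The endline cell lists 189. The row total is 567.
- **Full row of Table 5.** The midline cell carries the same 99 entry, but the expected midline rate is 75%.
- **Training-only row.** The rates are "expected: 50% baseline to 55% at midline to 50% at endline", and the midline cell reads "189 , midline-only comparison".
- **Note (b)**, on the endline 189: the aim is a 15-point difference at 80% power with ICC 0.01. "Training-only group value set at 50%, as this is most conservative. Intervention group value set at 65" percent.
- **Note (a)**, on non-inferiority between midline and endline: the size of 378 "is recommended for each time point in the full package group only". It uses a margin of 0.10, a level of 0.025, ICC 0.005 and 54 facilities.

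No note explains the 99. Hypothesis 2 is non-inferiority in the partial arm from midline to endline. Hypothesis 3 is partial against training-only at endline. The data analysis plan (section 4b5) restricts Hypotheses 3 and 4 to endline data.

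**The concern.** One sample size cannot serve both a 20-point difference (75% against 55%) and a 10-point difference (65% against 55%) at the same power. The repeated 99 therefore cannot be right in both rows.

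The same gap appears at endline, where it touches a stated hypothesis. Note (b) uses one calculation for either intervention arm, with the intervention rate at 65%. Table 4 puts the full arm above that (70%) and the partial arm below it (60%). The note calls its control rate conservative, but for the partial arm its intervention rate is optimistic.

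The partial arm isolates peer-led practice without mobile support, and the results are meant to inform scale-up advice to government. A reader who takes the stated 80% at face value could read a non-significant partial-arm result as evidence that peer practice does not work, when the plan's own rates give it about an even chance of detection.

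**Working it through.** **Inputs.** Rates are from Table 4. Power of 80% and ICC 0.01 are from note (b). Two-sided 0.05 is assumed, because the plan states no level for the between-arm comparisons. The 54 facilities in note (a) are taken as per arm, which the wording leaves open.

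**Formulas.**
- Size per arm, with p̄ the mean of the two rates: n = [1.960·√(2p̄(1−p̄)) + 0.842·√(p1(1−p1)+p2(1−p2))]² / (p1−p2)²
- Continuity correction: n_cc = (n/4)·[1+√(1+4/(n·|p1−p2|))]²
- Design effect: DE = 1+(births/54−1)·ICC
- Power: Φ{[|p1−p2|·√n − 1.960·√(2p̄(1−p̄))] / √(p1(1−p1)+p2(1−p2))}

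**1. Reproducing the plan's figures.**

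| Contrast | n | n_cc | n_cc × DE | Plan |
|---|---|---|---|---|
| 65% v 50% | 169.3 | 182.4 | 183 × 1.025 = 187.6 | 189 |
| 75% v 50% | 57.7 | 65.4 | 66 × about 1.01 = 66.6 | 67 |
| 75% v 55% | 88.1 | 97.8 | 98 × 1.008 = 98.8 | 99 |

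The n_cc values are rounded up before multiplying. The continuity-corrected formula with a small design effect comes within a birth or two of all three entries. So 99 is the size for the full arm's midline contrast.

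**2. The partial arm at midline, 65% v 55%.** Here p̄ = 0.60, 2p̄(1−p̄) = 0.480 and the unpooled sum is 0.475.
- n = (1.960·√0.480 + 0.842·√0.475)² / 0.01 = 375.6; n_cc = 395.3.
- With ICC 0.01 and 54 facilities, these become about 398 and 421.
- Even one-sided 0.05 needs 296 to 316. No variant comes near 99.
- Power with 189 per arm: 51%, or 50% with DE 1.025. With 99 in each arm it would be 30%.

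**3. The partial arm at endline, 60% v 50% (Hypothesis 3).** Here 2p̄(1−p̄) = 0.495 and the unpooled sum is 0.490.
- Power with 189: Φ[(0.10·√189 − 1.960·√0.495)/√0.490] = Φ(−0.006) = 49.8%, or 48.8% with DE 1.025.
- 80% power would need 387 per arm (407 with continuity correction).
- At note (b)'s 65% v 50%, 189 give 84%, so the note is right for its own inputs.

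**4. Non-inferiority in the partial arm (Hypothesis 2).** Note (a)'s margin of 0.10, one-sided 0.025 and ICC 0.005 are borrowed. DE = 1+(189/54−1)·0.005 = 1.0125. Power = Φ[(0.10−decline)/SE − 1.960], with SE = √{1.0125·[p1(1−p1)+p2(1−p2)]/189}.

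| Midline → endline | SE | Power |
|---|---|---|
| 65% → 65% | 0.0494 | 53% |
| 60% → 60% | 0.0507 | 50% |
| 65% → 60% (Table 4) | 0.0500 | 17% |

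**The case against.** Much can be said for the plan, and several points stand.

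- **The 99 sets no target.** A reader might infer that the partial arm's midline comparison will run at 30% power. The documents do not support that. The 30% needs 99 births in each arm, and Table 5 schedules 189 in both: the partial row total of 567 is 3 × 189, and training-only also lists 189. The planned power is about 50%.
- **The midline contrast answers no stated hypothesis.** Hypotheses 3 and 4 use endline data only, and Hypotheses 1 and 2 are within-arm. The 99 on its own cannot cause a wrong conclusion on any of the four.
- **Not every partial-arm comparison is weak.** The baseline-to-midline comparison, 50% to 65%, has 84% power with 189 at each time point (83% with DE 1.025).
- **Note (b) discloses its inputs.** It states the 15-point target and both rates, and 189 fits them. It does not say that Table 4 expects only 10 points for the partial arm.
- **The plan does not claim to size Hypothesis 2.** Note (a) is confined to the full arm, and the partial row lists no midline-to-endline comparison. But the hypothesis is stated without saying that it is not powered.
- **The Hypothesis 2 percentages rest on borrowed settings.** Section 4b5 describes a 90% interval, a 0.05 level and a margin of 0.06, for knowledge and competence scores. With margin 0.10 and one-sided 0.05, the 50 to 53% becomes 63 to 65%, and the 17% becomes 26%. Low power under an expected decline is also not peculiar to the partial arm: the full arm with 378 births, falling from 75% to 70%, has about 33%.

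That the 99 was carried over from the full row is an inference from the arithmetic. The documents do not say so.

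**Conclusion.** The point holds in limited form. The 99 in the partial row does not match that arm's own rates; about 376 to 395 births per arm would be needed, somewhat more with clustering. That error is confined to a table entry. The consequential part is Hypothesis 3: the stated 80% power falls to about 50% at Table 4's endline rates for the partial arm. Hypothesis 2 has no size calculation, and its power is about 50 to 53% at best and 17% at the expected decline if note (a)'s settings apply.

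The superiority figures assume two-sided 0.05. One-sided 0.05 would raise the 189-per-arm power to 63% at midline and 62% at endline, still below 80%. The clustering allowance assumes 54 facilities per arm and moves the results by only about one percentage point.

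**What to change.** Three text changes in section 3c:

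1. In the partial row of Table 5, delete the 99 or replace it with the size for 65% against 55% (about 376, or 395 with continuity correction), and state the level and ICC used.
2. In note (b), say that 80% power applies to a 15-point difference, and that 189 per arm give about 50% at the partial arm's Table 4 rates, at midline and at endline.
3. State that Hypothesis 2 on oxytocin is estimated with a confidence interval and is not powered.

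No births are added, and neither the design nor the analysis model changes. The cost is that the stated power for the partial arm becomes less favourable, and a non-significant partial-arm result will have to be reported with its interval and not as absence of effect.

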16	Semi-structured interview guide: Health care providers	Health care providers will be asked about their experiences with the program and their ideas for how to improve care for postpartum hemorrhage and neonatal asphyxia.
17	Semi-structured interview guide: Stakeholders	Stakeholder will be asked about their opinions about how to strengthen and sustain this program and other efforts to improve care for postpartum hemorrhage and neonatal asphyxia in Uganda.

3) *Number of study contacts* or visits required of participants.

Please see table 2 on page 5 for details. Briefly, women in labor, key stakeholders and facility in-charges will each have a maximum of only one study contact. Providers could have up to 12 study contacts, if they were selected for all types of data collection, but this will be rare. Similarly, peer practice coordinators could have up to 12 study contacts plus regular telephone contact with a member of the research team.

4) **Expected duration of the study.**

After JHSPH IRB and Ugandan IRB are obtained, the study will take 18 months.

5) A brief **data analysis plan** and description of the **nature of the variables** to be derived.

Primary Outcome:

- For the postpartum hemorrhage component, the primary outcome will be the proportion of women who received **oxytocin** (at correct dosage) within one minute of a vaginal birth, before delivery of the placenta. Data for this outcome will be obtained from the direct clinical observations.
- For the neonatal asphyxia component, the primary outcome will be the proportion of babies not breathing at birth who are breathing or being ventilated by one minute.

Secondary Outcomes:

- Change in providers' knowledge and competence related to postpartum hemorrhage and neonatal resuscitation, as assessed by knowledge tests and observed performance with a simulator.
- Trends in PPH and neonatal asphyxia/mortality rates, by abstracting *aggregated* monthly service statistics from each facility.
- Identification of structural, environmental and behavior factors that are associated with routine, frequent practice with the simulator.

Data will be entered using [name]/Foxpro/SPSS/CsPro and analyzed using Stata 12.

Quantitative data analysis

Specific Hypotheses:

In BAB and in HBB related to the primary outcomes (see Section 4b5):

1. Provider competencies and performance will not decline (i.e. will be non-inferior) between midline and endline in the *full* package group.

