2. Provider competencies and performance will not decline (i.e. will be non-inferior) between midline and endline in the *partial* package group.
3. At endline, the provider competency level and the performance level of the *partial* package group will be significantly higher than those of the training-only group.
4. At endline, the provider competency level and the performance level of the *full* package group will be significantly higher than those of the training-only group.

Hypotheses 1 and 2:

This is a non-inferiority analysis. Two-sided 90% confidence intervals (CI) for the difference in average knowledge and competence scores between midline and endline will be constructed, separately for full and partial package groups. Non-inferiority will be determined comparing the upper bound of the 90%CI for the difference between the 2 time points to the pre-specified non-inferiority margin of 0.06 (22). If the CI's upper bound is less than the predefined margin, then we are able to claim non-inferiority of the endline knowledge scores to the midline knowledge at a 0.05 level of significance.

We will first examine the differences in sample means of knowledge scores between midline and endline not adjusted for any potential confounding variables. The confidence intervals for the knowledge scores will be calculated using generalized linear models with knowledge and competencies as the dependent variables and time variable (endline vs. midline) as the primary independent variables. To account for repeated observations within providers at midline vs. endline, we will use robust Huber/White estimate of variance implemented in STATA through 'vce' (cluster) option. In addition, adjusted 90% CI for the difference in means will be constructed by adding provider- and facility-level factors in the model.

Hypotheses 3 and 4:

We will examine differences in competencies and performance at endline between the 3 study groups using generalized linear models. The dependent variables in these models will be:

- 1) knowledge and competency scores,
- 2) proportion of women who received **oxytocin** (at correct dosage) within one minute of a vaginal birth,
- 3) proportion of women whose placenta was inspected within 16 minutes, and
- 4) proportion of newborn checked for breathing within 1 minute.

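### Oxytocin outcome: the 80% non-inferiority power in Table 5 note (a) needs almost no decline and is about 33% at the tabulated fall from 75% to 70%; the partial arm's 45–49% power at endline is not disclosed

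*Combined protocol and SAP*

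**What the plan says.** **Non-inferiority, full arm (section 3c, Table 5 note (a)).** The note supports 378 births at midline and 378 at endline: "This sample size will achieve 80% power to detect a non-inferiority margin difference between the group proportions of providing oxytocin of -0.1000". It refers to the preceding table for the statement that "the percent of deliveries with oxytocin provision at midline (post-intervention) is hypothesized to be 70% in Full group", sets 54 facilities, and adds: "We assume intra-class correlation (ICC) of 0.005 and significance level of the test is 0.0250". It states no assumed true change between the two time points.

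**Hypothesised rates (Tables 4 and 5).** The row label in Table 5 reads "Full Intervention Group (expected: 50% at baseline to 75% at midline to 70% at endline". Table 4 has the same values. The partial arm is put at 50%, 65% and 60%, and the training-only arm at 50%, 55% and 50%.

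**Hypotheses (sections 1 and 4b5).** For the full package (Hypothesis 1) and the partial package (Hypothesis 2): "Provider competencies and performance will not decline (i.e. will be non-inferior) between midline and endline".

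**Analysis of Hypotheses 1 and 2 (section 4b5).** The text concerns knowledge and competence scores. Non-inferiority is judged by "comparing the upper bound of the 90%CI for the difference between the 2 time points to the pre-specified non-inferiority margin of 0.06", which is said to allow the analyst to "claim non-inferiority of the endline knowledge scores to the midline knowledge at a 0.05 level of significance".

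**Endline superiority (Table 5 note (b)).** The 189 births per group rest on this target: "We aim to detect a 15% point difference at endline between an intervention group and the training-only group". The inputs are 65% against 50%, 80% power and ICC 0.01. Table 5 attaches note (b) to the endline cell of all three arms.

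**The concern.** Note (a) misquotes the table it cites. The 70% it gives for midline is the endline value, so the planned 5-point fall drops out of the calculation. That fall uses up half of the 10-point margin, and non-inferiority power is very sensitive to it.

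Note (b) has a milder problem. Its 65% is neither intervention arm's tabulated endline rate (70% full, 60% partial). Hypothesis 3, partial against training-only, therefore rests on a difference of 10 points, for which no power is given.

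Timely oxytocin is a primary outcome. If the sponsor's own expectations came true exactly, the tests of Hypotheses 1 and 3 on this outcome would each be more likely to fail than to succeed, while the notes show only 80%. A reader relying on them could take a failed test as evidence of lost skill or of no benefit.

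**Working it through.** **Hypothesis 1: inputs.** From note (a): n = 378 per time point, margin 0.10, level 0.025 (taken as one-sided), ICC 0.005, 54 facilities. Rates come from Tables 4 and 5. Midline and endline births are treated as independent samples, since different women are observed.

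Design effect: 378/54 = 7 births per facility, so DE = 1 + (7 − 1) × 0.005 = 1.03.

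**Reproducing 378.** With 70% at both time points, n = (1.960 + 0.842)² × (0.21 + 0.21)/0.10² ≈ 330. Then 330 × 1.03 ≈ 340, or 340/54 ≈ 6.3 births per facility. Rounding up to 7 gives 7 × 54 = 378. The stated figure is thus recovered with equal rates.

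**Power at n = 378.** With midline rate pm and endline rate pe:

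SE = √{[pm(1 − pm) + pe(1 − pe)] × DE/378}; power = Φ{[margin − (pm − pe)]/SE − z}

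| Midline → endline | SE | Argument of Φ (margin 0.10, z = 1.960) | Power |
|---|---|---|---|
| 70 → 70 | 0.0338 | 0.10/0.0338 − 1.960 = 1.00 | 84% |
| 75 → 75 | 0.0320 | 0.10/0.0320 − 1.960 = 1.17 | 88% |
| 75 → 74 | 0.0322 | 0.09/0.0322 − 1.960 = 0.84 | 80% |
| 75 → 70 | 0.0329 | 0.05/0.0329 − 1.960 = −0.44 | 33% |

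The largest true decline that keeps 80% power is 1.0 point from 75%, or 0.5 point from 70%.

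**Sensitivity at 75 → 70.** The Farrington–Manning form gives 33.1%; ignoring clustering gives 33.8%; one-sided 0.05 with the 0.10 margin gives 45%. Reaching 80% would take about (1.960 + 0.842)² × 0.3975/0.05² ≈ 1,248 births per time point before clustering.

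**If the section 4b5 pair (0.06 and 0.05, z = 1.645) applied to oxytocin.** Power would be 55% at 70 → 70, 59% at 75 → 75 and 9% at 75 → 70. Under that pair, 80% would not be reached even with no decline.

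**Hypothesis 3: inputs.** From note (b): 189 per arm and ICC 0.01. The note gives no significance level, so two-sided 0.05 is assumed. It gives no facility count either, so 54 is taken from note (a): 189/54 = 3.5 births per facility, DE = 1 + 2.5 × 0.01 = 1.025, effective n = 189/1.025 = 184.4.

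**Reproducing 189.** For 65% against 50%, the pooled-variance formula gives 170 per arm, or 183 with continuity correction. Then 183 × 1.025 ≈ 188, against 189 stated.

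**Power.** Φ{(d − 1.960 × SE₀)/SE₁}, where d is the difference (reduced by 1/n with continuity correction), SE₀ uses the pooled rate and SE₁ the separate rates.

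- 65 v 50: SE₀ = 0.0515, SE₁ = 0.0509. Power is 83%, or 80% with continuity correction.
- 60 v 50: SE₀ = 0.0518, SE₁ = 0.0516. (0.10 − 0.1016)/0.0516 = −0.03, so power is 49%, or 45% with continuity correction.

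**Clustering.** Note (a) builds 54 from three districts in each of two regions. The allocation text in section 3 gives four districts per arm (2 regions × 2 groups of three districts, one district per arm in each group). Using 133/3 ≈ 44 facilities per arm changes little: 33% for 75 → 70 and 49% for 60 v 50 without continuity correction. The Hypothesis 3 figures allow for facility clustering only. Allocation is by district, so any positive between-district variation would lower them.

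**The case against.** **The arithmetic in both notes is sound, and non-inferiority trials are often sized at zero true difference.** This stands as far as it goes: 378 and 189 both follow from the notes' inputs, and replacing 70% by 75% at both time points would raise power. But note (a) does not state a no-decline assumption, and the table it cites shows a 5-point fall.

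**Hypothesis 1 speaks of no decline, so the assumption is implied.** The hypothesis itself glosses no decline as non-inferior, that is, as a loss within the margin. It is not a statement of the true difference assumed for power, and it cannot override a tabulated fall.

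**Note (b) states its target openly, and a detectable difference need not equal the expected one.** This is fair. The point on note (b) is non-disclosure, not error, and would not by itself require correction. The full arm's 70% against 50% (Hypothesis 4) is well powered, at about 98% with 189 per arm on the same facility-level basis.

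**The 0.06 margin is written for scores, so its use for oxytocin is hypothetical.** Different outcomes may carry different margins, and no text applies 0.06 to oxytocin. Yet Hypotheses 1 and 2 cover performance as well, and the analysis plan has no non-inferiority text for a performance outcome. Which pair governs needs to be stated.

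**Hypothesis 2 is lower still.** This is correct. With 189 births per time point and note (a)'s other inputs (DE = 1 + 2.5 × 0.005 = 1.0125), power is about 53% at 65 → 65 and 17% at the tabulated 65 → 60. It adds to the point and does not weaken it.

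**Conclusion.** The concern holds. Note (a) contradicts Tables 4 and 5 on the full-arm midline rate, and its 80% is not delivered at the plan's own hypothesised rates: power for Hypothesis 1 on oxytocin is about 33%. This rests on reading 0.025 as one-sided and on independent samples at the two time points; the one-sided 0.05 level would raise it only to 45%. For Hypothesis 3, power at the tabulated 60% against 50% is about 45–49%, assuming two-sided 0.05 and 54 facilities per arm; this is an upper figure because district-level variation is left out. The governing margin and level for the oxytocin test are not settled by the text. The note (a) error must be corrected; the other two items are secondary and belong in the same edit.

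**What to change.** 1. In note (a), give 75% at midline and 70% at endline. State that 80% power applies only to a true decline of about 1 point or less, and that power at 75% to 70% is about 33% at one-sided 0.025. If no decline is what was meant, change Table 4 and the Table 5 row label instead.
2. State which margin and significance level apply to the oxytocin non-inferiority test (0.10 and 0.025, or 0.06 and 0.05), and compute the stated power with that pair.
3. In note (b), state that 80% applies to a 15-point difference and that power for the partial arm's tabulated 10 points is about 45–49% under the note's facility-level ICC. Add that district-level clustering is not allowed for and would lower these figures.
4. In section 4b5, keep the pre-specified tests and report their confidence intervals. State that failure to show non-inferiority (Hypothesis 1) or superiority (Hypothesis 3) on oxytocin will not be read as evidence of skill loss or of no benefit.

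The Hypothesis 2 power can usefully be added in the same edit.

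The cost is rewording two table notes and adding two sentences to the analysis plan. No births or data are added. The price is that the stated power becomes less favourable.
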